10.3 Data entered directly in the CRF – definition of source data

Source Data are the clinical findings and observations, laboratory data maintained at the study site. Source data are contained in **source documents**. Local authorities are allowed to access the source data. Data will be entered directly onto the CRFs. The CRF is considered as a source document. All CRFs will be kept for at least 15 years.

The study site will retain the original of the CRF to ensure that local collaborators can provide access to the source documents to a monitor, auditor, or regulatory agency while a copy of the CRF will be taken to Swiss TPH.

10.4 Data and safety monitoring board/ data monitoring committee

In our study no data and safety monitoring board will be established, since we work with well-known drugs in a limited number of participants and using a single dose treatment. This study is anticipated to be no greater than minimal risk to participants.

- 33. ICH Expert Working Group: ICH harmonised tripartite guideline. Clinical safety data management: definitions and standards for expedited reporting E2A. International conference on harmonisation of technical requirements for registration of pharmaceuticals for human use; 1994.
- 34. Duggan MB: Anthropometry as a tool for measuring malnutrition: impact of the new WHO growth standards and reference. *Ann Trop Paediatr* 2010, **30**(1):1-17.
- 35. Wang Y, Chen H: Use of Percentiles and Z-Scores in Anthropometry. In: *Handbook of Anthropometry*. Edited by Preedy V. New York: Springer; 2012: 29-48.

Page 163 of 176

7. Statistical Analysis Plan (SAP)

Clinical trial protocol title:	Efficacy and safety of ivermectin and albendazole co-administration in school-aged children and adults infected with Trichuris trichiura : a multi-country randomized controlled trial
Principal Investigator	[name]
ClinicalTrials.gov identifier	03527732
Author	[name]
Version/Date	v1.0/14.9.2020

Page 164 of 176

Contents

Signatures	
Introduction	
Study Objectives and Endpoints	
Study Objectives	
Primary Objective	167
Secondary Objectives	
Study Endpoints	
Primary	
Secondary	
Statistical Hypotheses	
Study Design	
Planned Analyses	169
Interim Analyses	
Final Analysis	
Sample size consideration	
Populations for analysis	
Subgroup analyses	
Data handling conventions and missing data	
Protocol deviations	170
Demographics and other baseline characteristics	171
Efficacy analysis	171
Safety analysis	

Page 165 of 176

Signatures

The following persons have read and agreed on the SAP:

[name]

Trial Statistician

Date of signature 14.9.2020

[name]

Principal investigator

Date of signature 14.9.2020

[name]

Introduction

This Statistical Analysis Plan (SAP) is based on the current trial protocols versions v1.01_19.09.2018 (Lao PDR), v1.03_22.11.2018 (Côte d'Ivoire) and v1.01_13.2.18_(Zanzibar).

Where statistical methods differ substantially between this SAP and the protocol, the differences will be identified in the SAP.

This SAP describes the datasets and the statistical methods to be used for the reporting and analysis of all data collected 3 weeks after treatment in **three randomized controlled trials**. If a future protocol amendment necessitates a substantial change to the statistical analysis of the trial data, this SAP will be amended accordingly.

If, after database lock, deviations or additional analyses are required to supplement the planned analyses described in this SAP, those will not be described in an amended SAP, but they will be identified in the related publication.

This SAP has been written in consideration of the following guidelines:

- International Conference on Harmonization (ICH) E9, Guidance for Industry: Statistical Principles for Clinical Trials (ICH E9 1998)1
- ICH E3, Guidance for Industry: Structure and Content of Clinical Study Reports (ICH E3 1995)

Statistical analysis will be done using R 5.3.1 on a Windows 64 bit system.

Page 167 of 176

Study Objectives and Endpoints

Study Objectives

Primary Objective

To assess the efficacy and safety of standard doses of co-administered ivermectin (200 μ g/kg) and albendazole (400 mg) against *Trichuris trichiura* compared to albendazole (400 mg) alone in community members aged 6-60 years.

Secondary Objectives

To evaluate the safety and tolerability of the treatment regimens

To compare the egg reduction rate (ERR) of the treatment regimens against T. trichiura

To determine the CRs and ERRs of the drugs in study participants (6-60 years) infected with hookworm, *Ascaris lumbrico*ides and *Strongyloides stercoralis*

Study Endpoints

Primary

T. trichiura cure rate (CR) defined as infection status assessed by Kato-Katz 14-21 days after treatment expressed as cure rate, i.e. conversion from being egg positive pre-treatment to egg negative post-treatment.

Secondary

ERR against T. trichiura

CRs and ERRs against A. lumbricoides, hookworm and S. stercoralis

Adverse events

Infection status assessed by PCR

Safety

Statistical Hypotheses

Primary hypothesis: albendazole-ivermectin has a higher efficacy against *T. trichiura* infections compared to albendazole alone.

Study Design

This is a multi-center, blinded, randomised, SoC-controlled, parallel-group, single-dose, superiority trial. Participants in the albendazole monotherapy arm will receive a matching ivermectin placebo. Double blinded (study participants, trial team/researchers conducting the treatment and outcome assessors) using repacked tablets including appearance-matched placebos. Computer-generated stratified block randomization code. The random allocation sequence with varying random blocks of four or eight and stratified by 2 levels of baseline infection intensity. Tablets together with the respective treatment arm label were pre-packed by researchers not involved in this trial into small opaque envelopes labelled with the unique IDs to ensure allocation concealment.

Time and Events Table

	Screening	Baseli	ne/Tr	eatment/	Safety	Follow up						
	-21 to -1		Η	lours		Days						
	days	0		3	24	21	180 ^a	185ª	360ª			
Diagnosis (stool and urine examination)	Х					Х	Х		Х			
Gut morbidity (stool RDTs)	Х					Х	Х		Х			
Informed consent	Х		ent									
Demographics	Х		eatmo									
Medical history		Х	nd tr					ment				
Clinical examination		Х	ion a				Х	treat	Х			
Pregnancy testing		Х	mizat				Х	ve re-				
Hemoglobin measurement		Х	opue				Х	electiv	Х			
Plasmodium co-infection		Х	ß				Х	Š	Х			
Venous blood examination		Х				Х	Х		Х			
Physical functioning		Х					Х		Х			
Capturing AEs				Х	Х	Х						
Capturing SAE				Х	Х	Х						
Treatment satisfaction				Х		Х	Х					

^a not subject of this SAP

Page 169 of 176

Planned Analyses

Interim Analyses

Because of the short follow-up period, no interim analyses are planned.

Final Analysis

The database will be locked after all subjects have completed the study and the data have been entered, validated and all queries are resolved.

Sample size consideration

Each of the three trials was powered to detect a difference with 90% power at a two-sided 5% significance level assuming a CR of albendazole against *T. trichiura* is 30% and 50% in the albendazole-ivermectin treatment regimen. We anticipate to enrol 143 participants per study arm (including a potential loss to follow-up of 15%). For sub group analysis the data from all trials will be pooled to ensure sufficient power. Further details on the justification of study subjects are provided in the trial protocols.

Populations for analysis

Available case population: All participants randomized, excl. those who entered the study even though they did not satisfy the entry criterion 'positive at baseline' with at least one non-missing endpoint data.

Per protocol population: All participants who meet all inclusion and exclusion criteria, have no major protocol deviations and received the correct treatment.

Intention to treat population: All participants randomized, excl. those who entered the study even though they did not satisfy the entry criterion 'positive at baseline'

Safety population: All subjects who received at least one dose of treatment with at least one non-missing safety endpoint with no major protocol deviations.

Efficacy endpoints will be analysed using the available case population according to the ITT principles. The primary analysis will be confirmed using the per-protocol population. Safety endpoints will be analysed using the safety population as treated.

Subgroup analyses

The following pre-specified sub group analyses will be conducted:

- by age category (6-12 years vs. 13+ years)
- by baseline infection intensity (light vs moderate & heavy)

For sub group analyses the data from all trials will be pooled to ensure sufficient power.

Data handling conventions and missing data

All subjects who withdraw prematurely from the study or study drug will be included in the statistical analyses. Experience from previous trials indicated that the proportion of missing data is usually below 10%; therefore, no imputation of missing data is planned. In case the proportion of missing data will be considerably higher than expected the primary analysis using the available case population will be complemented by an analysis using the

Page 170 of 176

intention-to-treat population. For this purpose missing data will be imputed by multiple imputations as implemented in R's 'mi' package.

Protocol deviations

Before closing the database, data listings will be reviewed to identify any significant deviations and determine whether the data should be excluded from any analysis populations.

Protocol deviations leading to exclusion from all analyses populations

• Participants who were negative for *T. trichuria* infection at baseline.

Major protocol deviations include subjects who:

- Entered the study even though they did not satisfy other entry criteria.
- Met the criteria for withdrawal from the study but were not withdrawn.
- Received no treatment, the wrong treatment or incorrect dose.
- Received an excluded concomitant therapy.

Minor protocol deviations include subjects who:

- Provided fewer stool samples than specified in the protocol
- Provided stool samples later than specified in the protocol (measurements taken outside the allowable windows given in the protocol)
- Vomiting within 1-hour post-dosing without re-treatment.

Participants with major protocol deviations will be excluded from the per-protocol population. Minor protocol deviations will remain in all analysis populations.

Page 171 of 176

Demographics and other baseline characteristics

Baseline characteristics will be calculated and presented as outlined below

	Pemb	a Island	Côte d	'Ivoire	Lao PDR		
Characteristics	ALB (n=xxx)	IVM-ALB (n=xxx)	ALB (n=xxx)	IVM- ALB (n=xxx)	ALB (n=xxx)	IVM- ALB (n=xxx)	
Age, 6-12							
Age, 13-24yrs							
Age, 25 years and above							
Sex, n (%)							
Females							
Males							
Weight, kg							
Height, cm							
T. trichiura infection							
Geometric mean EPG							
Infection intensity ^a , n (%)							
Light							
Moderate							
Heavy							
A. lumbricoides infection							
Infected, n (%)							
Geometric mean EPG							
Infection intensity ^b , n (%)							
Light							
Moderate							
Неаvy							
Hookworm infection							
Infected, no. (%)							
Geometric mean EPG							
Infection intensity ^c , n (%)							
Light							
Moderate							
Неаvy							
S. stercoralis infection ^d							
Infected, n (%)							

^a *T. trichiura* infection intensity classified according to mean eggs per gram of stool (EPG) into: light=1-999 EPG, moderate=1000-9999 EPG and heavy=≥10000 EPG

^b A. lumbricoides infection intensity classified according to mean eggs per gram of stool (EPG) into: light=1-4999 EPG, moderate=5000-49999 EPG and heavy=≥50000 EPG

^c Hookworm infection intensity classified according to mean eggs per gram of stool (EPG) into: light=1-1999 EPG, moderate=2000-3999 EPG and heavy=>4000 EPG

^d Baermann technique to detect *S. stercoralis* infection was only applied to stool samples collected in Lao PDR

Page 172 of 176

In the unadjusted analysis the differences in cure rates will be assessed using a Melded Binomial Confidence Intervals and Tests with mid-p correction as implemented in the 'exact2x2' package.

library(exact2x2)
binomMeld.test(... , # insert n[pos] and n[total]
parmtype = "difference", conf.level = 0.95, conf.int = TRUE,
alternative = "two.sided", midp = T)

This analysis has been chosen because most biomedical journals prefer the absolute difference over the relative difference. However, adjustment for confounder or effect modifier is not possible; therefore, the adjusted analysis will use standard logistic regression.

Egg reduction rates (geometric mean based) will be calculated using the following formula

$$ERR = 1 - \frac{\frac{1}{n}e^{\sum \log(EPG_{follow} - up + 1)}}{\frac{1}{n}e^{\sum \log(EPG_{baseline} + 1)} - 1}$$

Differences in geometric mean based ERR will be analysed via bootstrap resampling using the following code

}

library(boot) difgm <- boot(data = d, statistic = diffgm, R = 2000, strata = d\$arm)

The arithmetic based ERR will be estimated in the same way.

If the sample size of study participants infected with hookworm, Ascaris lumbricoides and *Strongyloides stercoralis* is considered sufficiently large, efficacy against these parasites will be assessed in the same way. If the number of participants will be below 100 per arm the trial arms will only be compared descriptively.

Page 173 of 176

Efficacy results and estimates will be presented as outlined below

		Pemba Is	land	Côte d'Iv	oire	Lao PDR		Total		
Variab	le	ALB (n=xxx)	IVM- ALB (n=xxx)	ALB (n=xxx)	IVM- ALB (n=xxx)	ALB (n=xxx)	IVM- ALB (n=xxx)	ALB (n=xxx)	IVM- ALB (n=xxx)	
T. trich	iura									
No. of p	participants positive	for								
infectio	n Defere									
	treatment									
	After treatment									
Cure ra	te. % (95% CI)									
No. of p	participants cured n	(%)								
1	From light									
	From moderate									
	infection									
	From heavy									
Carrier	infection									
Geomet	tric mean EPG									
	Before									
	After treatment									
GMEg	g_reduction rate									
% (95%	CI)									
Arithme	etic mean EPG									
	Before									
	treatment									
	After treatment									
AM Eg	g-reduction rate,									
% (95%) A lumb	o CI) bricoid e s									
N partic	cinants positive									
T partic	Before									
	treatment									
	After treatment									
Cure ra	te, %									
N partic	cipants cured (%)									
1	From light									
	infection									
	From moderate									
	infection									
	From heavy									
Geomet	tric mean EPG									
	Before									
	treatment									
	After treatment									
Egg-red	luction rate, %									
Hookw	orm									
N partic	cipants positive	1								
	i 1			1		1		1		

Page 174 of 176

	Before					
	treatment					
	After treatment					
Cure rat	e, %					
N partic	ipants cured (%)					
	From light infection					
	From moderate infection					
	From heavy infection					
Geometric mean EPG						
	Before treatment					
	After treatment					
Egg-red	uction rate, %					
S. sterce	oralis ^a					
No. of p infection	participants positive	for				
	Before treatment					
	After treatment					
Cure rat	e, %					

EPG: eggs per gram of stool

^a S. stercoralis infection was assessed qualitatively only (positive vs negative) in stool samples collected in Lao PDR

Page 175 of 176

Safety analysis

Adverse events will be analysed descriptively and summarized (for each country) as outlined in the 2 tables below.

Table: Adverse events assessed at baseline, 3 hours and 24 hours post treatment by treatment arm

	Before treatment	3h post treatment	24h post treatment	After 24h
ALB				
Total participants assessed				
Participants with AE				
% participants with AE				
Number of AEs				
IVM-ALB				
Total participants assessed				
Participants with AE				
% participants with AE				
Number of AEs				
TOTAL				
Total participants assessed				
Participants with AE				
% participants with AE				
Number of AEs				

Page 176 of 176

	Baseline					3h post-treatment					24h post-treatment							
	AL	B	IVN	1-	ΤΟ	ГА	AL	B	IVN	1-	TO	FAL	AL	B	IVN	1-	тот	AL
			ALI	B	L				ALI	3					ALI	B		
Adver	N	N	N	N	N	N	N	N	N	Ν	N	N	N	N	N	N	N	N
se	A	Gr	A	Gr	A	Gr	A	Gr	A	Gr	An	Gr	A	Gr	A	Gr	An	Gr
event	nv	ad	nv	ad	nv	ad	nv	ad	nv	ad	v	ad	nv	ad	nv	ad	v	ad
event	gr	e	gr	e	gr	e	gr	e	gr	e	gr	e	gr	e	gr	e	gra	e
	ad	>2	ad	>2	ad	>2	ad	>2	ad	>2	ad	>2	ad	>2	ad	>2	de	>2
	e		e		e		e		e		e		e		e		au	
							-		-		-		-		-			
Heada																		
che																		
Abdo																		
minal																		
pain																		
Itching																		
Nause																		
а																		
Vomiti																		
ng																		
Diarrh																		
ea																		
Fever																		
Allergi																		
C																		
reactio																		
n																		
11																		
Other																		

Table: Specific adverse events by treatment arm and time point

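### The SAP's safety population drops dosed participants with major protocol deviations, so their adverse events miss the planned tables and the as-treated rule has nobody to reassign

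*Combined protocol and SAP*

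**What the plan says.** Four parts of the SAP bear on this.

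- **Populations for analysis** defines the set: "Safety population: All subjects who received at least one dose of treatment with at least one non-missing safety endpoint with no major protocol deviations". It then assigns the endpoints to that set: "Safety endpoints will be analysed using the safety population as treated".
- **Protocol deviations** lists the major deviations. Besides a failure to withdraw someone who met the withdrawal criteria, they are: "Entered the study even though they did not satisfy other entry criteria"; "Received no treatment, the wrong treatment or incorrect dose"; "Received an excluded concomitant therapy". On the consequence it says: "Participants with major protocol deviations will be excluded from the per-protocol population". It adds: "Minor protocol deviations will remain in all analysis populations".
- The same section has a separate rule, headed "Protocol deviations leading to exclusion from all analyses populations", for participants who were negative for *T. trichiura* at baseline.
- **Safety analysis** plans two descriptive AE tables for each country, by arm. No other AE set or listing is planned.

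Safety appears in the SAP's primary objective and again as a secondary objective.

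**The concern.** A safety population normally contains everyone who was exposed. Here a condition that belongs to a per-protocol set has been attached to it. The people removed are those whose events a safety summary most needs to show: participants given the wrong regimen or an incorrect dose, those who took a prohibited medicine alongside it, and those who should not have been enrolled. The entry criteria in section 5.3 of the country protocols concern, among other things, pregnancy, severe anaemia and serious chronic disease.

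The rule also runs the wrong way round. Someone who vomited within an hour and was not re-dosed has only a minor deviation and stays in every population, although the drug may not have been retained. Someone given an incorrect dose is dropped.

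**Working it through.** The plan states no figure for this point, so the main check is to apply the definition to each category. The arithmetic after that only illustrates scale.

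**1. Membership of the safety population, as defined**

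| Dosed participant | Deviation class | In the SAP safety set? | Would as-treated move the person to the other arm? |
|---|---|---|---|
| No deviation | none | yes | no |
| Vomited within 1 h, not re-dosed | minor | yes | no |
| Given the other regimen | major | no | yes |
| Incorrect dose | major | no | only if it amounted to the other regimen |
| Other entry criterion unmet | major | no | no |
| Excluded concomitant therapy | major | no | no |
| Should have been withdrawn | major | no | no |
| Baseline-negative | removed from all populations | no | no |

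The only rows where treatment received can differ from treatment assigned are rows already excluded. Within the defined set, as-treated and as-randomised groupings are therefore identical.

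**2. The data would exist.** AE capture is scheduled at 3 hours, 24 hours and day 21. Section 5.4 of each country protocol continues AE monitoring in discontinued participants, including those stopped for non-compliance. A discontinued participant is affected here only if one of the listed major deviations also applies.

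**3. Number removed.** The tables are per country, so counts are per arm and country. Sample sizes: n = 143 (SAP, Sample size consideration) and n = 300 (section 7.2 of the protocols). The share d of major deviators is assumed. Removed = n × d.

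- n = 143: 1.43, 2.86 and 7.15 at d = 1%, 2% and 5%.
- n = 300: 3, 6 and 15.

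**4. Shift in the reported AE proportion.** Let p be the AE risk in non-deviators and RR × p the risk in deviators (RR assumed, 0.5 to 2). The true proportion is p(1 − d + d·RR) and the reported one is p, so reported/true = 1/(1 − d + d·RR).

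| d | RR 0.5 | RR 1 | RR 2 |
|---|---|---|---|
| 1% | 1.005 | 1.000 | 0.990 |
| 2% | 1.010 | 1.000 | 0.980 |
| 5% | 1.026 | 1.000 | 0.952 |

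The between-arm AE ratio is unchanged if d and RR are equal in both arms. If all deviators are in one arm, it changes by the single factor in the table.

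**5. Loss of individual severe events.** Suppose k participants in the set being tabulated have an AE above grade 2. The share of them removed is s = d·RR/(d·RR + 1 − d), and P(at least one missing) = 1 − (1 − s)^k. With RR = 1, s = d:

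| k | d = 1% | d = 5% |
|---|---|---|
| 1 | 1.0% | 5.0% |
| 2 | 2.0% | 9.8% |
| 5 | 4.9% | 22.6% |
| 10 | 9.6% | 40.1% |

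For k = 5 and d = 5%, the figure is 12.2% at RR = 0.5 and 39.4% at RR = 2.

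**The case against.** The best reply is that the SAP, read as a whole, may not intend the exclusion. Protocol deviations names only the per-protocol population as the one major deviators leave. The SAP also says that premature withdrawals are included in the analyses, and that listings will be reviewed before the database closes to decide who leaves which population. The AE table shells name no population.

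None of this overrides the definition. The per-protocol sentence does not say that no other set is affected. The withdrawal sentence covers people who leave early, not deviators. The pre-lock review decides exclusions and does not create an AE listing. The shells are tied to the restricted set by the sentence that assigns safety endpoints to it. What stands is that this is an unreconciled inconsistency, so the finished tables might not follow the literal text.

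The objection on size is stronger. The deviation rate, the risk ratio and the number of severe events are all assumed. Supervised dosing from pre-packed envelopes may keep deviations rare, and sections 6 and 9.2 of the country protocols expect few and mainly mild AEs. Small k is then the more plausible case, with a chance of loss between 1% and about 10% for one or two events. A dosed baseline-negative participant should also be uncommon, since entry requires at least two positive slides and 100 EPG.

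**Conclusion.** The concern holds. As written, the definition keeps dosed major deviators out of the only planned AE tables and leaves the as-treated rule without effect. This follows from the text and needs no assumption about rates. The size and direction of any bias are unknown. Under the assumed ranges (d of 1% to 5%, RR of 0.5 to 2), AE proportions range from 2.6% too high to 4.8% too low in relative terms, so the main loss would be of individual severe events.

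The consequence is limited to descriptive tables. AE recording, SAE notification, reporting to authorities and the primary efficacy inference do not depend on this population. It should be fixed because safety is a stated objective and the correction is simple.

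**What to change.** In the SAP, **Populations for analysis**, delete the final five words of the safety definition (the condition on major deviations). Include every participant who received any study treatment and has at least one safety assessment, grouped by treatment received and regardless of baseline egg status. State explicitly how an incorrect dose is grouped, for example under the drugs actually taken, with a flag. Report how many dosed participants had no safety assessment, flag deviators, and add one listing of their AEs.

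In **Protocol deviations**, state that major deviations remove participants from the per-protocol population only, and exempt the safety population from the baseline-negative rule.

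The cost is a few sentences and one listing, with no new data. If the database is already locked, the SAP Introduction provides for deviations and additional analyses to be identified in the publication.

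A separate point should be settled as well. Section 6.1.4 of the Pemba protocol ends SAE reporting at 24 hours after treatment. The Pemba visit schedule (4.6) and the SAP Time and Events Table place SAE capture at day 21 too, and Pemba 6.1 and 6.2 set a day-21 AE window and a week-3 AE interview. These passages must be reconciled. If this is handled as a protocol amendment, it needs sponsor signature and ethics committee submission under section 8.1.

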4.3.2 Assessment of efficacy and other benefits after treatment

Parallel group multi-country and DF study

The efficacy of the treatment will be determined 21 days post-treatment by collecting another two stool samples which will be microscopically examined for *T. trichiura* using duplicate Kato-Katz thick smears and potential co-infection with *S. stercoralis* applying the Baermann technique. Participants will be considered *T. trichiura* cured if no eggs have been found in the stool. EPG will be assessed by adding up the egg counts from the quadruplicate Kato-Katz thick smears and multiplying this number by a factor of six. Geometric and arithmetic mean egg counts will be calculated for the different treatment arms before and after treatment to assess the corresponding ERRs. The stool samples collected 21 days post-treatment for efficacy assessment will further be re-tested with the same rapid diagnostic test and immunoassay used at baseline to determine fecal occult blood and calprotectin levels. Frequencies of subjects found positive with either of the two markers and by intensity category for calprotectin will be calculated by treatment arm.

At the end of the study (*i.e.* for exclusive DF study participants 1 month post-treatment, for trial participants 12 months post-treatment) all participants remaining positive for *T. trichiura*, other soil-transmitted helminths or filariasis will be treated with albendazole-ivermectin, the currently best approved and recommended treatment against *T. trichiura* [29].

Parallel group multi-country study

Potential extended effects on follow-up helminth prevalences will be assessed using the same methodological approach as used for the efficacy assessment and will be based on stool samples collected 6 and 12 months post-treatment. Likewise fecal occult blood and calprotectin will be re-determined on the same stool samples.

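### Does the SAP need a separate egg-count rule for participants who give only one stool at follow-up?

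*Combined protocol and SAP*

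**What the plan says.** Follow-up asks for two stools with duplicate 41.7 mg smears from each, so four slides (protocol sections 4.3.1 and 4.3.2, all versions). EPG is obtained by "adding up the egg counts from the quadruplicate Kato-Katz thick smears and multiplying this number by a factor of six" (section 4.3.2, repeated in section 7.3 of every version).

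The SAP, under Protocol deviations, lists among minor deviations subjects who "Provided fewer stool samples than specified in the protocol", and adds: "Minor protocol deviations will remain in all analysis populations". Under Populations for analysis, the available-case set needs a randomised, baseline-positive participant "with at least one non-missing endpoint data". Under Data handling, "no imputation of missing data is planned" unless missingness is considerably higher than expected.

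Geometric ERR is a secondary result. The SAP's efficacy section then says "The arithmetic based ERR will be estimated in the same way", and for the other helminths, if numbers suffice, "efficacy against these parasites will be assessed in the same way". The SAP gives no multiplier of its own. Footnotes to its baseline table class infection intensity by mean EPG.

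**The concern.** The plan foresees participants with one follow-up stool and keeps them everywhere, including the per-protocol set, yet its only conversion from counts to EPG assumes four slides. Someone who programmed the sum times six without checking how many slides had been read would record half the expected EPG for every one-stool participant. Follow-up means would fall and ERR would rise for a reason unrelated to treatment. The per-protocol analysis would not show it, because these people stay in that set too, and the planned tables do not report slides read. ERR would then depend partly on how many people brought a second stool.

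**Working it through.** **Factor.** EPG multiplier = 1000 mg / (slides × 41.7 mg).

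- Four slides: 1000 / 166.8 = 5.995. The protocol's factor of 6 is reproduced.
- Two slides: 1000 / 83.4 = 11.99, so 12.
- Factor 6 on two slides gives 6 / 11.99 = 0.50 of the expected EPG.
- 24 × the mean count per slide equals the sum times six with four slides and the sum times twelve with two.

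**What the text permits for two slides.** There are three codings: average the slides read, set EPG to missing, or keep the factor of six. Only the third halves EPG. Membership of the available-case set does not settle the choice, because a known cure status is itself a non-missing endpoint. A participant can be in the set without having an EPG.

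**Size under the third coding.** Let f be the share with one stool at follow-up, unrelated to egg count. The documents do not give f (the SAP's below-10% remark concerns missing data). I assume 10%, range 5% to 20%.

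*Geometric ERR, combination arm.* Inputs are each trial's means and cure counts in Table 2 of the protocol background. New follow-up mean = (GM + 1) × 2^(−f × p) − 1, where p is the proportion not cured. This slightly overstates the shift, since EPG + 1 does not fully halve. At f = 10%:

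| Trial | Before/after | p | New follow-up mean | ERR |
|---|---|---|---|---|
| Pemba 2015 | 489 / 27 | 79/109 = 0.725 | 28 × 2^(−0.0725) − 1 = 25.63 | 94.48% → 94.76% |
| Pemba 2010 | 127 / 11 | 87/140 = 0.621 | 12 × 2^(−0.0621) − 1 = 10.49 | 91.34% → 91.74% |
| Philippines | 550.0 / 1.9 | 52/149 = 0.349 | 2.9 × 2^(−0.0349) − 1 = 1.83 | 99.65% → 99.67% |

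The shifts are 0.01 to 0.40 points (0.01 to 0.20 at f = 5%; 0.02 to 0.78 at f = 20%).

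*Arithmetic ERR.* New ERR = 1 − (1 − ERR)(1 − f/2).

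- Combination, Pemba 2015 (1059 / 153): 153 × 0.95 / 1059 = 0.137, so 85.6% becomes 86.3%.
- Albendazole at 49.9% (Table 1, type of mean not stated, treated here as arithmetic): 0.501 × 0.95 = 0.476, so 52.4%. The 2.5-point shift lies well inside that estimate's own interval of 39.0 to 60.6.
- With equal f in both arms, the between-arm difference is multiplied by 1 − f/2. It loses 5% of its size (2.5% to 10% over the range).

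**Baseline.** The minor-deviation item is not limited to follow-up. If the same coding met one-stool participants at both visits with equal f, the arithmetic effect would cancel: (1 − f/2)/(1 − f/2) = 1. For 489/27 at f = 10%, the baseline mean becomes 490 × 2^(−0.1) − 1 = 456.2, and ERR = 1 − 25.63/456.2 = 94.4%, marginally below the correct value. Equal f is unlikely, because entry relies on quadruple smears, but net overstatement is not certain even under this coding.

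**Primary endpoint.** Cure means no eggs found, so the factor is irrelevant. Two slides detect less than four. If a share m of four-slide positives is missed on one stool, equally in both arms, the planned difference (50% against 30%) becomes 20 + 100 × f × m × (0.5 − 0.7). At f = 10% this is 19.9 points for m = 5% and 19.6 for m = 20%.

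**The case for a change.** The strongest case for acting is that the sum times six is the only conversion written down, that the mean-EPG footnotes concern baseline classes and carry no factor, and that ERR is reported by country, where randomisation does not balance stool compliance. If f were 5% in one country and 20% in another, a true arithmetic ERR of 49.9% in both would read 1 − 0.501 × 0.975 = 51.2% and 1 − 0.501 × 0.90 = 54.9%, a spurious gap of nearly 4 points. A line in the SAP would prevent this at almost no cost.

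It is true that the two-slide rule is unwritten, and that no other passage strictly rules out the bad coding. But the country gap arises only if an analyst applies a four-slide factor to two slides without noticing, and several features make that unlikely. Section 10.2 requires missing data to be explained and procedures not done to be marked as such, so an unread slide should be distinguishable from a zero count. The SAP has data listings reviewed for deviations before the database is closed. The analysis is in R, where a sum over a missing value is itself missing by default. The SAP's stated hypothesis compares arms, not countries. Under blinding there is no reason to expect stool compliance to differ by arm.

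**Conclusion.** The plan can stand. It omits a convention for a secondary endpoint that a competent analyst supplies without instruction: 24 times the mean count over the slides read, which changes nothing for complete samples. The feared bias needs a coding that the protocol's own wording does not support. If it did occur, combination-arm geometric ERR would rise by 0.01 to 0.40 points and the arithmetic contrast between arms would lose about 5% of its size, at an assumed 10% one-stool share, independent of egg count and equal across arms. Averaging would not make the data perfect either, since two slides give more zeros than four. That is a limit of the sample collected, not of the plan. The primary cure comparison is not materially affected.
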